This study will evaluate a new technology called the Carotid Stenotic Scan (CSS) developed by CVR Global, a medical device company. The CSS device uses principles of cardiovascular resonance to detect low frequency pressure fluctuations associated with

flow disturbances in areas of significant arterial narrowing. The CSS device consists of three non-emitting (passive) piezoelectric sensors contained in a cushioned gel pad, linked through a Y-shaped collar that positions one sensor over each carotid artery and one sensor on anterior central chest in the area of the heart (figure). These device pads lie on the skin surface and do not emit any energy into the body; they only gather data transmitted from within the body. The piezoelectric sensors in the device detect very low frequency pressure fluctuations generated by altered hemodynamics caused by narrowing

of the carotid artery. The CSS scan takes about 1-2 minutes to gather data for real-time analysis by the processor on the device cart.

Description: Prospective study of evaluable patients presenting to the Cleveland Clinic Non-Invasive Laboratory for a clinically indicated complete carotid duplex ultrasound examination. We aim to enroll 300 subjects. We will enroll at least 100 patients who have moderate stenosis of one ICA based on prior ultrasound studies and up to 25 patients with known carotid FMD. Subjects who enroll in the study will undergo evaluation by both carotid duplex ultrasound and the CSS device. Carotid duplex studies will be read by a registered physician in vascular interpretation, blinded to the CSS device result, and degree of ICA stenosis will be determined according to velocity criteria adopted by Cleveland Clinic Non-Invasive Vascular lab. Findings from CSS device will be analyzed and degree of ICA stenosis will be categorized.

Objectives:

1. To determine agreement of degree of internal carotid artery narrowing as measured by the CSS device versus carotid duplex ultrasound.
2. To determine the reproducibility measures of carotid artery narrowing as measured by the CSS device.
3. To compare the degree of carotid artery narrowing as measured by the CSS device versus any other imaging modality used to evaluate the internal carotid artery (CTA, MRA or catheter based angiography) (pilot analysis)

4. Exploratory data regarding CSS device output in the setting of carotid artery occlusions and fibromuscular dysplasia (FMD).

Study Subjects:

The study population will consist of adult patients (≥ 18 years) presenting to the Cleveland Clinic Non-Invasive Vascular Laboratory for a scheduled carotid duplex ultrasound to evaluate for carotid artery disease or in follow-up of known ICA stenosis. By design, we will enroll at least 100 patients who are known to have at least moderate stenosis of one ICA (i.e., PSV ≥ 125 cm/sec based upon the findings of prior imaging studies. In addition, a subset of up to 25 patients enrolled will include those with previously documented fibromuscular dysplasia of at least one ICA. Potentially eligible patients will be approached in the area where the ultrasound testing will be done by a qualified member of the study team prior to the ultrasound examination to explain the study and obtain appropriate informed consent.

Inclusion Criteria:

- Outpatients age ≥ 18 years sent to the vascular laboratory for carotid duplex examination for initial carotid ultrasound study or for follow-up of known carotid disease.
- Enrolled patients will include at least 100 subjects with at least moderate known stenosis (50-69% or greater, PSV ≥ 125 cm/sec) or occlusion of one or both ICAs
- Up to 25 patients with **known** fibromuscular dysplasia (FMD) of the internal carotid arteries.

Exclusion criteria:

- Age < 18 years.
- Hospitalized inpatients.
- Inability to provide informed consent.
- Prior history of carotid endarterectomy or carotid artery stent.
- Prior neck surgery
- Known prosthetic heart valve, known critical aortic stenosis, or study indication “preop” open heart or aortic surgery.

Study Visit Procedures: The research study will be conducted on the same day of the clinical carotid duplex study but may be performed prior to or after the scheduled carotid ultrasound (and any other vascular) examination(s), depending upon the patient schedule. After informed consent is obtained, limited medical history will be obtained, and self-reported height and weight will be recorded. The patient will undergo the standard of care carotid duplex examination and the CSS study procedure. Each subject will have a unique identifier number assigned that will be used on all ensuing study documents.

Medical History:

Data will be obtained by limited subject questionnaire and review of the electronic medical record, to include:

- Age on date of the study
- Sex
- Race, ethnicity
- Height and weight (self-reported)
- Study indication (first carotid duplex in lab, surveillance of known carotid artery stenosis, fibromuscular dysplasia, other)
- Treated medical conditions, including:
- Coronary artery disease (History of myocardial infarction, angina + abnormal stress test, or prior coronary artery bypass grafting or stenting/PCI)
- History of congestive heart failure
- Left ventricular ejection fraction (if known and date of echocardiogram within the past 1 year)
- Known peripheral artery disease (PAD)
- History of transient ischemic attack
- History of stroke
- Did patient have TIA, stroke or symptoms of retinal ischemia within 30 days of ultrasound study
- Hypertension requiring medication therapy
- Hyperlipidemia requiring medication therapy
- Diabetes requiring medication therapy or diet
- History of smoking cigarettes (> 100 in lifetime)
- Known diagnosis of fibromuscular dysplasia
- Known history of internal carotid artery dissection
- History of COPD
- Any correlative imaging studies (CTA, MRA, angiography) within 1 month prior to the day of the carotid duplex examination

Follow-up and Correlative Examinations:

Within 3 months (+/- 7 days) following the date of the study visit, the electronic medical record will be queried for any interval correlative imaging studies (CTA, MRA, or angiography) and reports performed up to 1 month prior and 3 months after the duplex examination date. Report of findings will be document (i.e., % ICA stenosis by CTA/MRA).

Study Procedures (Appendix B)**Standard Clinical Procedures:**

The subject will undergo the clinically ordered clinical carotid duplex ultrasound as part of standard of care. Studies are performed using a standardized scanning protocol (Appendix C) by a Registered Vascular Technologist and interpreted by a Registered

Physician in Vascular Interpretation or otherwise qualified member of the medical staff. The vascular technologist and interpreting physician will be blinded to the output of the CSS study device.

- For purposes of this study, degree of ICA stenosis will be reported according to SRU consensus velocity criteria., Primary SRUCC parameter to determine % ICA stenosis will be peak systolic velocity, unless there is a clear indication for the use of a secondary parameter (ICA/CCA ratio, EDV), such as contralateral occlusion, tandem lesions, discrepancy between visual assessment of the plaque and PSV and others(4).

SRU Consensus Criteria (4)

| Primary Parameters | | Secondary Parameters | | |
|-----------------------------------|----------------------------|------------------------------|-------------------|------------------|
| Degree of stenosis (%) | ICA PSV (cm/sec) | Plaque Estimate (%)* | ICA/CCA PSV Ratio | ICA EDV (cm/sec) |
| Normal | < 125 | None | <2.0 | <40 |
| < 50 | < 125 | <50 | <2.0 | <40 |
| 50-69 | 125-230 | ≥50 | 2.0-4.0 | 40-100 |
| ≥ 70 but less than near occlusion | >230 | ≥50 | >4.0 | >100 |
| Near occlusion | High, low, or undetectable | Visible | Variable | Variable |
| Total occlusion | Undetectable | Visible, no detectable lumen | Not applicable | Not applicable |

*Plaque estimate (diameter reduction) with gray-scale and color Doppler US.

- Degree of stenosis per the Cleveland Clinic Non-invasive Vascular Laboratory will also be recorded (ECST based):
 - 0-19% stenosis PSV < 105 cm/sec no plaque
 - 20-39% stenosis PSV < 105 cm/sec plaque visualized
 - 40-59% stenosis PSV 105 – 150 cm/sec
 - 60-79% stenosis PSV > 150 cm/sec but EDV ≤ 135 cm/sec
 - 80-99% stenosis PSV > 240 cm/sec and EDV > 135 cm/sec
 - Occlusion – absent flow on extensive Doppler interrogation
 - Ultrasound features of carotid FMD (increased velocity and turbulent flow mid to distal ICA).

The following ultrasound parameters will be recorded for each side:

- Distal CCA peak systolic velocity
- Highest origin/proximal to mid ICA peak systolic velocity (PSV)
- Associated end diastolic velocity (EDV) for highest PSV
- ICA/CCA PSV Ratio
- Presence of plaque in the ICA (defined as wall thickness ≥ 1.5 mm)
- Presence of distal ICA waveform dampening (qualitative)

- Presence of post-stenotic spectral and/or color Doppler turbulence
- SRU Consensus Criteria % ICA Stenosis
- Cleveland Clinic Criteria % ICA Stenosis

For FMD subset: highest ICA mid/distal PSV and associated EDV

CSS Study Procedures:

Subjects will have a noninvasive CSS assessment as described below before or after the carotid duplex ultrasound. It is expected that the entire CSS evaluation will take approximately ten minutes. See Appendix A for the CSS Study Procedure.

Study Data Collection

Each subject will have a hard copy file with case report information and source documents, medical history questionnaire, CSS output, and the ultrasound reports. These individual files will be maintained with identifiers, including the signed consent form, and maintained in a locked filing cabinet accessible to the study coordinator and the authorized investigators. A Redcap database will be developed and maintained for clinical data entry and this will be housed on a password-protected network. All data that the sponsor receives will either be aggregate data or de-identified case report files. Deidentified ultrasound images and de-identified correlation study images and report may be requested by the sponsor for cases in which CSS results and duplex findings were discrepant.

Statistical Analysis Plan and Power Calculation: Primary analysis % agreement CSS and carotid duplex ultrasound (SRUCC interpretation) for ICA stenosis. Agreement will be assessed using the intraclass kappa coefficient (and corresponding 95% confidence intervals) for categorical data. Percent stenosis from both the CSS measurement and the duplex ultrasound will be categorized as follows:

| Carotid Duplex by SRU Consensus | Simplified Duplex Category by SRU Consensus | CSS Device |
|---------------------------------|---|------------------|
| Normal | <50% | <50% |
| <50% | <50% | <50% |
| 50-69% | 50-69% | 50-69% |
| ≥70% | ≥70% | ≥70% |
| Occlusion | Occlusion | Exploratory data |
| U/S Features of FMD | FMD | Exploratory data |

It is anticipated that approximately 40% of total patients will have an ICA stenosis of 50% or greater. A sample of at least 300 patients (up to 500 carotid arteries) will have 90% power to detect an intraclass correlation coefficient of 0.80, assuming a null hypothesis of 0.65, with a 2-sided alpha of 0.05.

The secondary endpoint of reproducibility of the CSS measurement will be analyzed using the continuous stenosis measurement. Each CSS measurement will be repeated and the Intraclass Correlation Coefficient (ICC) will be calculated. The ICC is an index of the reliability of measurements from the same operator. Pearson and/or Spearman correlation coefficients and plots may also be produced.

Separate exploratory analyses will address the following:

- 1) Correlation of CSS results to duplex ultrasound results in those with ICA by duplex occlusion
- 2) Correlation of severity of stenosis from CTA, MRA, or catheter based angiography (when available) to CSS results.
- 3) Correlation of CSS stenosis results to duplex ultrasound results in those with known ICA FMD (approximately 25 patients)

Data and Safety Monitoring

This protocol poses no physical risk and the need for a formal Data Safety and Monitoring Board (DSMB) is not anticipated. However, reporting of any adverse events will follow the standard procedures of Cleveland Clinic. The only risk to the subject is loss of confidentiality and this will be protected to the best of the sponsor's ability.

Potential Risks: This is a low risk protocol. The CSS device is non-invasive and passive and does not cause any discomfort. The only risks relate to confidentiality and the study team will minimize these risks as discussed above. In the unlikely event of a study-related adverse event, the Principal Investigator, IRB and CVR Global will be notified.

Potential Benefits

There will be no direct benefit to the subject for participation, though study participants will receive a parking pass. There may be benefit to society as a whole when the accuracy and efficacy of the device as a rapid, noninvasive means to diagnose carotid artery disease has been shown.

REFERENCES

3. de Weerd M, Greving JP, Hedblad B, Lorenz MW, Mathiesen EB, O'Leary DH, et al. Prevalence of asymptomatic carotid artery stenosis in the general population: an individual participant data meta-analysis. *Stroke*. 2010;41(6):1294-7.

[figure not shown]

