Note: When a patient does **not have plaque present**, but has **elevated velocities** throughout the ICA and the CCA (i.e., normal ICA/CCA ratio <2) the statement **"elevated velocities, no plaque seen. Likely normal study"** will be used in place of calling a category of stenosis.

Note: Although our criteria are based upon PSV and EDV, ICA/CCA ratios are included on our reports. These **criteria are added** for use in interpretation of cases in which **PSV may not accurately reflect the degree of stenosis** (e.g., tandem lesions in innominate or CCA, contralateral occlusion, and elevated velocities in all vessels due to underlying cardiac disorder). In general, an ICA/CCA ratio of > 4 is suggestive of a $> 70\%$ stenosis (NASCET criteria).

Note: In the setting of a contralateral ICA occlusion, there is potential for overestimation of stenosis due to compensatory flow. This should be noted in the interpretive report when appropriate (e.g., velocities in 80-99% category contralateral to occlusion).

II. Common carotid artery interpretation:

50-99% stenosis Velocity shift with doubling of PSV across an area of plaque

III. External carotid artery interpretation:

Elevated velocities, plaque noted PSV > 200 cm/sec with significant plaque visualized

IV. Subclavian artery interpretation:

50-99% stenosis Velocity shift with doubling of PSV across an area of plaque or PSV > 275 cm/sec in proximal subclavian artery with turbulent flow and plaque noted

If turbulent flow is present but no plaque is visualized, findings may suggest more proximal subclavian artery stenosis

REFERENCES

Cleveland Clinic internal validation studies of carotid ultrasound examinations and angiograms.

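### Does the protocol leave the duplex reference category for the primary agreement analysis open, by naming two sets of criteria and giving near occlusion no row?

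*Protocol*

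**What the plan says.** The Description, in its overview of the study, states that "degree of ICA stenosis will be determined according to velocity criteria adopted by Cleveland Clinic Non-Invasive Vascular lab".

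Study Procedures, under Standard Clinical Procedures, states: "For purposes of this study, degree of ICA stenosis will be reported according to SRU consensus velocity criteria". PSV is the leading parameter there. The reader may turn to secondary parameters when there is clear reason, and one listed reason is that the plaque as seen does not fit the PSV. After the SRU table the protocol adds: "Degree of stenosis per the Cleveland Clinic Non-invasive Vascular Laboratory will also be recorded (ECST based"). The SRU and laboratory gradings then appear as two separate items in the list of recorded ultrasound parameters.

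The section Statistical Analysis Plan and Power Calculation opens with "Primary analysis % agreement CSS and carotid duplex ultrasound (SRUCC interpretation) for ICA stenosis". Both duplex columns of its category table are labelled as SRU consensus.

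The SRU table labels its top graded band "≥ 70 but less than near occlusion" and gives near occlusion a row of its own: "Near occlusion | High, low, or undetectable | Visible | Variable | Variable". The primary category table has no such row. It goes from ≥70% straight to "Occlusion | Occlusion | Exploratory data".

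In Appendix C, Diagnostic Criteria, a note covers raised velocities without plaque and with a normal ICA/CCA ratio. A statement that the study is probably normal "will be used in place of calling a category of stenosis".

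**The concern.** The reference category decides whether each CSS reading counts as an agreement or a disagreement, so two competing reference standards would be serious. The laboratory bands have no boundary at 50% or at 70%, the two cuts of the primary table. A grade read under the Description could not be placed in that table.

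Near occlusion raises a separate worry. If PSV alone were followed, a low-flow near occlusion would have PSV below 125 cm/sec and would fall in the <50% class, although it is among the most severe patent lesions. Even if it is recognised as near occlusion, the primary table does not say whether it enters the kappa as ≥70% or leaves it with the occlusions. If that were decided after the CSS results were known, the choice could favour the device.

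Finally, the laboratory's probably-normal statement appears to clash with a PSV-led SRU grade of 50-69% for the same artery.

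**Working it through.** **1. The plan's own figure.** The stated power is 90% for 0.80 against 0.65 with at least 300 patients. I used the goodness-of-fit formula for a binary intraclass kappa with two ratings, prevalence p = 0.40, q = p(1−p) = 0.24 and D = q(0.80−0.65) = 0.036.

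- Non-centrality per unit: D²/(p²+0.65q) + (2D)²/(2q(1−0.65)) + D²/((1−p)²+0.65q) = 0.00410 + 0.03086 + 0.00251 = 0.03747.
- Units needed for 90% power: (1.960+1.282)²/0.03747 ≈ 281.
- Power at 300: Φ(√(300×0.03747) − 1.960) = 91.8%.

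This agrees with the stated 90%, if the 40% patient-level prevalence is applied to each unit. The calculation takes no input from the wording at issue.

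**2. The two scales on the same measurements.** I applied the PSV and end-diastolic velocity (EDV) cut-points in Study Procedures, grading SRU by PSV.

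| PSV (cm/sec) | EDV (cm/sec) | SRU | Laboratory |
|---|---|---|---|
| 110 | ≤135 | <50% | 40-59% |
| 135 | ≤135 | 50-69% | 40-59% |
| 200 | ≤135 | 50-69% | 60-79% |
| 235 | ≤135 | ≥70% | 60-79% |
| 300 | 140 | ≥70% | 80-99% |

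The laboratory's 40-59% band covers two SRU classes, and so does its 60-79% band. The scales therefore cannot be interchanged. For the same reason the laboratory scale cannot produce a second version of the three-class primary table.

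**3. Which scale governs.** The Description names the laboratory scale but does not mention the primary analysis. Standard Clinical Procedures names SRU for the study and the laboratory grade as an addition. The statistical section names SRU for the primary analysis and in its column headings. The enrolment threshold for moderate stenosis (50-69% or greater, PSV ≥125 cm/sec) is also the SRU cut. Only the Description departs, and the section that defines the analysis is explicit.

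**4. Low-flow near occlusion as <50%.** This needs PSV to be followed without exception. The protocol departs from PSV when plaque and PSV do not fit. The SRU row allows a high, low or undetectable PSV with visible plaque, so a low PSV does not make the artery <50%.

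**5. Raised velocities without plaque.** The Appendix C note requires no plaque and a ratio below 2. In the SRU table these are the Normal-row values, whereas 50-69% goes with plaque of at least 50% and a ratio of 2.0-4.0. The plaque exception covers this artery, and the SRU grade is recorded separately from the laboratory's statement.

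**6. What remains.** A recognised near occlusion has two possible destinations, ≥70% or exploratory occlusion. Suppose m of N graded arteries are near occlusions. Of the other n = N−m, a agree; of the m, x agree. Including them changes percent agreement by (x − m·a/n)/N, which is at most m/N in absolute value. For m = 1 this is 1/500 = 0.20 percentage points at N = 500 and 1/300 = 0.33 at N = 300. The protocol gives no value for m and no class counts, so no corresponding figure for kappa can be derived.

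**The case for a change.** The strongest case rests on near occlusion. The statistical section prints the mapping itself, so it has not simply been left to another document, and the printed mapping is incomplete. Reading ≥70% as a plain number does not fully settle the matter, because the SRU label expressly stops that band short of near occlusion. The secondary parameters named in Standard Clinical Procedures do not help either, since the SRU table lists the ICA/CCA ratio and EDV as variable for this class. The laboratory scale has no such class. An assignment made with the CSS results in view could be biased, and writing it down would cost one line.

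Much of this stands as description. No velocity parameter assigns the class, and the table is silent. But the reader assigns it from the SRU row and the image, blinded to the CSS output. The open step is only which row of the analysis table receives it. ≥70% is the more natural choice for a vessel that is still patent, and separate reporting with the occlusions is also defensible. Neither choice contradicts another statement in the protocol.

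On the two criteria, the objection is right that the Description conflicts with later text. It does not show that any artery would change primary category.

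**Conclusion.** No change to the plan is needed. The Description sentence is a clerical inconsistency: the analysis section fixes the SRU reading as the primary reference, and the laboratory grade is kept alongside it. The examples at PSV 110, 135 and 235 compare two separately recorded scales and move no artery in the primary table. The <50% scoring of near occlusion and the clash with the probably-normal statement do not hold, given the plaque exception and the SRU table's own rows.

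The missing near-occlusion row is a real but small gap of the kind analysts fill sensibly. Its size is at most 0.20 to 0.33 percentage points of simple agreement per such artery, taking 500 or 300 graded arteries. The effect on kappa and the number of near occlusions cannot be obtained from the protocol.

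This rests on two assumptions: that the duplex reader uses the SRU near-occlusion row as printed, and that the row assignment for analysis is made without reference to the CSS readings. PSV, EDV, ratio, plaque and distal waveform dampening are all recorded, so either assignment can be applied and the other checked alongside it.

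### The record query for correlative imaging may be run up to 7 days before the 3-month imaging window it has to cover has closed

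*Protocol*

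**What the plan says.** The protocol's section Follow-up and Correlative Examinations sets the timing of a medical-record search: "Within 3 months (+/- 7 days) following the date of the study visit, the electronic medical record will be queried". In the same sentence, the search is to find interval imaging and "reports performed up to 1 month prior and 3 months after the duplex examination date".

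Four other places bear on the point:

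- Study Visit Procedures ties the visit to the duplex: "The research study will be conducted on the same day of the clinical carotid duplex study".
- The Medical History list separately collects correlative imaging from the month before the duplex, at the visit.
- Objective 3, which uses these images, is labelled a pilot: "CTA, MRA or catheter based angiography) (pilot analysis".
- The analysis is listed among the exploratory ones in Statistical Analysis Plan and Power Calculation: "Correlation of severity of stenosis from CTA, MRA, or catheter based angiography (when available) to CSS results".

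The protocol states no second search, and the visit checklist in Appendix B does not mention the search at all.

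**The concern.** A search can find only what has been performed and filed by the day it is run. If it may be run before the imaging window closes, images from the last part of the window can be missed by staff who follow the protocol exactly. How much of the window is covered would then depend on the day each record was opened, so that no imaging found would not mean quite the same thing for every subject.

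At stake is the completeness of the post-visit CTA, MRA and angiography results available for comparison with the CSS device. Images from before the duplex are less exposed, since the medical history collects them too. The instruction is one that the protocol itself fixes, and a later analysis document could not recover images that were never looked for.

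**Working it through.** The protocol gives no figure for this point, so there is nothing to reproduce. The check is date arithmetic.

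**Inputs**

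- Day 0 is both the study visit and the duplex (Study Visit Procedures).
- W is the day on which the imaging window closes, 3 months after the duplex. The protocol does not convert months to days, so I assume W = 91 and check 90 and 92.
- q is the day of the query. As a visit window it runs from W - 7 to W + 7.
- The pre-duplex month is taken as 30 days (assumption), so the whole window is 30 + 91 = 121 days.

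**Formula**

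Days not yet elapsed at the query = max(0, W - q). The share of the post-duplex window is that number divided by W.

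**Visit-window reading, W = 91**

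| Query day | Days unseen | Share of post-duplex window | Share of whole window |
|---|---|---|---|
| 84 (-7) | 7 | 7/91 = 7.7% | 7/121 = 5.8% |
| 91 (on time) | 0 | 0% | 0% |
| 98 (+7) | 0 | 0% | 0% |

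With W = 90 the early-edge share is 7/90 = 7.8%; with W = 92 it is 7/92 = 7.6%.

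**Average rather than worst case**

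If query days were spread evenly over the 14-day tolerance (assumption), half would fall early with a mean shortfall of 3.5 days and half would lose nothing. The mean loss is 0.5 × 3.5 = 1.75 days, which is 1.75/91 = 1.9% of the post-duplex window and 1.75/121 = 1.4% of the whole.

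**Deadline reading, W = 91**

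If *within* meant any day up to the limit, a query at day 60 would leave 91 - 60 = 31 days unseen (31/91 = 34%), and one at day 30 would leave 61 days (61/91 = 67%).

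All of these are shares of calendar days. They would equal shares of scans only if scans were spread evenly over the window, and the protocol gives nothing from which to judge that.

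**The case against.** The strongest reply is that the sentence, read as a whole, describes a chart check at about 3 months with a week's tolerance. A query on the due day or up to 7 days later complies and sees the whole window. This stands: the rule allows a loss and does not impose one. A reader might infer that late scans are bound to be lost, but the text does not support that.

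A reader might also take the 67% from the deadline reading as the size of the problem. That reading leaves the minus half of the tolerance without a function, and a day-30 query could not do what the same sentence asks of it. I show the figure only to mark what the loose wording would literally admit.

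Nor does objective 3 rest on this search alone, because the medical history already collects imaging from the month before the duplex. The protocol also does not forbid a repeat search; it simply states none.

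Finally, the consequence is small. The analysis correlates paired measurements where they exist; it does not estimate an event rate, so it does not need equal follow-up. Nothing ties the query date to the CSS result, so no bias is shown. Images missed at the early edge would be among those furthest in time from the CSS scan. All of this stands and limits the weight of the point. It does not remove the mismatch: the minus side of the tolerance lets a compliant query come too soon for its stated task.

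**Conclusion.** The point holds as a minor defect of wording. A compliant query can precede the close of the window it must cover, by at most 7 of about 91 post-duplex days on the natural reading. That is 7.7% in the worst case for one subject, and 1.9% on average if query days are evenly spread. The number of images lost is unknown and may be zero.

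The conclusion rests on the visit and duplex sharing a date, on 3 months being 90 to 92 days, and on no further search being made. The effect is confined to post-visit imaging for the pilot objective 3 and its exploratory correlation. The primary agreement analysis, the reproducibility analysis and the sample size are untouched.

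**What to change.** Move the tolerance to the plus side. State that the record is queried no earlier than 3 months after the duplex date, for example at 3 months with -0/+14 days, for studies from 1 month before to 3 months after the duplex. The plus side also leaves time for reports to be filed; -0/+7 days would close the gap as well, with less allowance for late reports. There is no need to limit the search to a single occasion.

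The cost is one sentence and no extra patient contact. With the 14-day tolerance, the latest query falls 14 - (-7) = 21 days, about three weeks, after the earliest day now allowed on the visit-window reading.

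### The correlative-imaging window can pair a scan taken after carotid endarterectomy or stenting with a CSS reading of the untreated artery (pilot objective 3 only)

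*Protocol*

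**What the plan says.** Objective 3 of the protocol, labelled a pilot analysis, reads in part: "To compare the degree of carotid artery narrowing as measured by the CSS device versus any other imaging modality used to evaluate the internal carotid". Four statements determine which values enter that comparison.

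- **When CSS is measured.** Study Visit Procedures: "The research study will be conducted on the same day of the clinical carotid duplex study". Appendix A repeats the scan once at the same visit. No later CSS reading is planned.
- **Which images are retrieved.** Follow-up and Correlative Examinations: the electronic record is searched for "any interval correlative imaging studies (CTA, MRA, or angiography) and reports performed up to 1 month prior and 3 months after" the duplex date. The reported percentage of ICA stenosis is then documented.
- **How they are used.** Second item in the list of separate exploratory analyses: "Correlation of severity of stenosis from CTA, MRA, or catheter based angiography (when available) to CSS results". Availability is the only condition stated.
- **How treated arteries are handled.** The exclusion criteria, repeated in the Appendix B checklist, bar "Prior history of carotid endarterectomy or carotid artery stent". This applies at enrolment.

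The Medical History list, the follow-up paragraph and the Appendix B checklist contain no item for a carotid procedure performed after the study visit.

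**The concern.** CSS describes the artery on one day. The image may describe it up to 3 months later. If the artery was opened by endarterectomy or stenting in between, the two values refer to different anatomy, and their disagreement says nothing about the device.

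The disagreement would not be random. The study is enriched for disease: "Enrolled patients will include at least 100 subjects with at least moderate known stenosis (50-69% or greater, PSV ≥ 125 cm/sec) or occlusion". The urgent-value list in Appendix C also sends the tightest lesions straight to the ordering provider. It is a fair inference, though not a statement in the documents, that arteries treated within 3 months would mostly be severe ones. Those are the arteries where a high CSS value would then meet a low imaging value.

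At stake is the only comparison in the protocol between CSS and an imaging method other than duplex.

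**Working it through.** **Step 1: does the text admit the pairing?** Take an artery with severe stenosis at the visit, treated at week 4 and imaged by CTA at week 8.

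- The patient had no procedure before enrolment, so the exclusion does not apply.
- The CTA falls within 3 months after duplex, so it is retrieved and its percentage stenosis documented.
- The exploratory correlation asks only that an image be available, so the CTA qualifies.
- No data item marks the procedure.

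The pairing is therefore allowed as written.

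**Step 2: direction.** The protocol gives no figure for this comparison to reproduce, and no rate of interval treatment or later imaging. Everything numerical below is assumed. Let true stenosis be normal with mean 60 and SD 18, and let CSS and imaging each add independent error with SD 9. Without treated arteries:

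r = 18² / (18² + 9²) = 324 / 405 = 0.80.

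Now let a share f of pairs come from arteries with true stenosis of at least 70, imaged after treatment at mean 10, SD 8. The cut-off lies (70 − 60)/18 = 0.556 SD above the mean, and the normal tail ratio there is 1.182. For these arteries:

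- mean excess over 60: m = 18 × 1.182 = 21.3
- mean squared excess: m₂ = 324 × (1 + 0.556 × 1.182) = 536.8

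Then

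- Cov = 324 − f(m₂ + 50m)
- Var(image) = 405 − f(m₂ + 81) + f(50² + 8²) − [f(m + 50)]²

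At f = 0.05:

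- Cov = 324 − 80.0 = 244.0
- Var = 405 − 30.9 + 128.2 − 12.7 = 489.6
- r = 244.0 / √(405 × 489.6) = 244.0 / 445.3 = 0.55

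The same formulas give 0.69 at f = 0.02, 0.35 at f = 0.10 and 0.01 at f = 0.20. A simulation of this model, with true stenosis limited to 0–99, gives 0.69, 0.54, 0.35 and 0.01.

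The covariance term shows why the direction is fixed. If treated arteries lie above the average stenosis and their later images below it, each such pair reduces the covariance.

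**Step 3: a second set of assumptions.** Take 40 arteries, 60% with stenosis of 50% or more and true values uniform within each stratum. CSS error SD is 10 and imaging error SD 8. Treated arteries come from the tightest 20 and are read afterwards at 0–20%. Mean correlations by simulation:

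| Arteries imaged after treatment | Pearson | Spearman |
|---|---|---|
| 0 of 40 | 0.91 | 0.89 |
| 1 of 40 | 0.84 | – |
| 2 of 40 (5%) | 0.78 | 0.77 |
| 4 of 40 (10%) | 0.67 | 0.65 |
| 8 of 40 (20%) | 0.47 | 0.42 |

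Rank correlation does not remove the effect.

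**Step 4: what the two sets show together.** Both fall in the same direction. At 5% they give 0.78 and 0.55, and at 10% they give 0.67 and 0.35. The size therefore depends on the assumptions. It also depends on the measure: in the Step 2 model, three-category agreement falls only from 65% to 62% at 5% and to 58% at 10%.

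**The case against.** The best defence is that the follow-up paragraph says what to collect, not what to analyse. Rules for pairing images with CSS in a pilot analysis could sit in a statistical analysis plan that is not shown here. The setting also points to untreated arteries: prior endarterectomy, stenting and neck surgery are excluded, and the Appendix C examination protocol is titled for native arteries. Reports are retrieved as well, so a treated side might be recognised at analysis. The window also admits images from before treatment, which both illustrations ignore, since each treated artery there has only a later image.

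Part of this stands. The intention was very probably to study native arteries, and the illustrated sizes cannot be taken as forecasts. It does not remove the gap. The protocol itself sets the imaging window and the data collected, and the only analysis condition it states is availability. A later plan could exclude post-procedure images only if they could be identified. No procedure date is planned, and the sponsor receives only aggregate or de-identified data. A second look at the records could recover the dates, but that is avoidable work.

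Three stronger readings are tempting and are not supported:

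- **That treated arteries would be counted as CSS errors.** No error count or accuracy threshold is planned for objective 3. They would enter as discordant pairs in a correlation.
- **That this will happen.** It requires treatment and then CTA, MRA or angiography of the same artery within 3 months, and the documents do not say how often that occurs. The statement that "It is anticipated that approximately 40% of total patients will have an ICA stenosis of 50% or greater" describes disease, not treatment.
- **That the main result is at risk.** The primary CSS-duplex agreement uses same-day measurements, and reproducibility uses two scans at one visit. Neither uses correlative imaging.

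**Conclusion.** The point holds in a limited form. The correlative-imaging rule as written lets a post-procedure image be compared with a CSS reading of the untreated lesion, and nothing planned for collection would reveal it. If such pairs occur, they lower the apparent CSS-imaging correlation. That direction rests on three assumptions: that CSS tracks stenosis to some degree, that treated arteries are more stenosed than average, and that their later images show less than average stenosis. The size cannot be derived from the documents. The falls shown above illustrate that a few pairs could matter in a small sample and do not estimate what this study would see.

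Only objective 3 is affected, and it is a pilot comparison without a hypothesis or power statement. The point is minor.

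**What to change.** Make two additions to Follow-up and Correlative Examinations:

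1. At the record query already planned, record the date and side of any carotid endarterectomy or stenting performed after the study visit.
2. State that the objective 3 comparison uses, for each artery, only imaging done before any such procedure on that side.

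If several images qualify for an artery, choosing the one nearest the CSS date is a sensible optional detail. Leaving it out is not part of the error.

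The cost is one sentence and one small data item in an existing query. The downside is a few fewer pairs in a pilot analysis. The change concerns only which data are recorded and compared, and it leaves patient care and the primary analysis as they are.
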